1.7 Privacy

All data obtained from study participants will be coded and not passed on to other people. Personal data and personal details are stored in paper form in a locked filing cabinet. The head of the research laboratory and at the same time the head of the study has access here, and the administration of the documents also falls within his area of responsibility.

All digital data is encrypted and encoded. No conclusions can be drawn about individuals. The digital data is stored on internal computers, archived and not released to outsiders.

Employees involved in data processing have no insight into the personal data and the coding of it.

1.8 Other committees or institutes involved

The study is being conducted in the research laboratory at the University of Applied Sciences and Arts Southern Switzerland, Physiotherapy Graubünden, [name], Switzerland.

The test products and measuring equipment are all located in this room and therefore all measurements can be carried out at the same location. The room offers enough space.

At present, no further studies with this arrangement are taking place in this experimental laboratory. Another study is currently taking place at our institute (NCT 02847663). However, the measurements of these two studies do not take place at the same time and do not hinder or influence each other. Thus, the utilization of the infrastructure is not excessive and therefore justifiable.

No other institutes and committees are involved in this study or in the approval or monitoring of the study.

SUPSI

2 ETHNIC & REGULATORY ASPECTS

2.1 Study Registration

The implementation of the present study is the responsibility of the Cantonal Ethics Committee Zurich. An application for admission is submitted. Any further conditions of the responsible ethics committee must be implemented in the study protocol.

When the study protocol is submitted to the Cantonal Ethics Committee in Zurich, the study is also registered with the Swiss Coordination Office for Research on Human Subjects. In addition, the study is registered in a WHO-recognized primary registry (clinicaltrials.gov ID: NCT03016221).

2.2 Categorization of the study

The study is categorized as a clinical trial with intervention products of risk category A (ClinO, Art. 20). The subjects are given over-the-counter topical products, warming products based on wintergreen oil, cooling products based on menthol and/or alcohol. Neither tissue samples nor other invasive methods are performed. Measurements are carried out with CE-certified equipment according to their instructions for use.

2.3 Competent Ethics Committee (CEC)

Human research in the Canton of Graubünden falls under the remit of the Cantonal Ethics Commission Zurich. Changes to the study protocol are not permitted without the prior consent of the CEC, except for the immediate elimination of obvious hazards to the participants. According to chap. 2.10 to the CEC.

An early termination or interruption of the study must be reported to the CEC within 15 days, and the regular end within 90 days. The final report must be submitted within one year of the end of the programme. Corrections are to be reported in accordance with Chapter 2.10.

2.4 Competent Authorities (CA)

The present study falls under the remit of the Cantonal Ethics Committee Zurich. Obligations and deadlines can be found in the previous point.

2.5 Ethical Leadership of the Study

The study will be conducted in accordance with this protocol and the current version of the Helsinki Declaration, the ICH-GCP, the European Medical Device Directive 93/42/EEC and the ISO standard 14155 and ISO 14971 (where applicable), as well as the Swiss Human Research Ordinance and thus Swiss law.

The CEC receives an annual report and is informed about the course of studies.

2.6 Conflict

There is no financial conflict of interest on the part of the sponsor/investigator, nor is there a corresponding relationship of dependency.

SUPSI

2.7 Patient information and informed consent

The examiners will explain to each participant individually the nature of the study, its content, intent and objective. This includes the protocol flow, approximate time duration, possible risks and benefits. The participant is informed that participation is voluntary and can be withdrawn from the study at any time, without personal consequences of any kind. The participant will be informed about data protection, the handling of personal data and their access.

Each participant receives written subject information and the declaration of consent with the detailed study description and all necessary information to be able to decide whether to participate in the study. The participant will also be given sufficient time to read this written information and to ask questions to the responsible examiners.

The subject information and the informed consent form are submitted to the CEC, where they must be reviewed and approved.

The signed declaration of consent must be submitted before the start of the study process. The participant should read them before signing and check their contents. The responsible examiner then also signs the declaration of consent. Finally, the participant receives a copy of the declaration of consent. The signed declaration of consent is kept in the original as a study document in a locked filing cabinet.

2.8 Confidentiality & Privacy

The examiners ensure that the privacy of the participants is maintained. In particular, data protection and confidentiality are guaranteed, and no personal data is presented or published. The signed declaration of consent, as well as the completed questionnaire with the other personal details, are kept in the original as a study document in a locked filing cabinet.

The digital data is encrypted and treated confidentially, and access to the personal data is denied to third parties. The digital data collected is stored solely on the institute's own computers and is not passed on to any external persons or transferred to other computers.

Direct access to the personal data is allowed only to the head of the research laboratory (study leader), as well as authorized persons of the CEC.

2.9 Early termination of the study

The sponsor or principal investigator may discontinue the study early if/

- ethical concerns
- insufficient number of subjects
- the safety of the participants cannot be guaranteed
- Findings from clinical practice make it pointless to continue the study
- early evidence or harm of the experimental intervention has been proven

2.10 Adjustments to the protocol

Adjustments and changes to the current study are only permissible after review by the CEC.

SUPSI

Short-term changes to the protocol prior to an audit by the CEC may be made to ensure the rights and safety of participants. However, such adjustments must be documented and reported to the CEC as soon as possible.

Significant changes are only permissible after a review of the CEC. Any other changes must be notified to the CEC as soon as possible and listed in the annual report.

SUPSI

3 BACKGROUND AND RATIONALE

3.1 Background and justification

The use and application of topical products for local pain relief in chronic or acute musculoskeletal apparatus complaints are widespread. The advertising propagates corresponding products from various pharmaceutical manufacturers with pain-relieving and circulation-promoting effects. The products used here are available without a prescription in online shipping or in stores. The field of application and the information on the application are contained in the insert. The application forms vary from sprays to gels to plasters. Science is extensively concerned with the field of application and effectiveness of topical NSAID products on chronic pain in osteoarthritis^{2,3}. Topical products have the advantage over oral medications of bypassing the gastrointestinal tract and thus avoiding possible side effects¹. Derry et al. 2016 describe in their review that topical NSAIDs achieve significant pain relief compared to placebo treatment in subjects with osteoarthritis². The authors found no significance for other chronic pain conditions. Matthews et al. 2011 showed that topical applications with a hyperemic effect (ingredient salicylates) were not successful in acute injuries and therefore recommended topical NSAID products for chronic pain conditions⁵. Several studies with different forms of application have been able to achieve pain relief through the use of topical NSAIDs^{4,6,12,13}.

Lasanen et al. 2016 tested different menthol concentrations of a cooling gel for skin cooling and concluded that all tested concentrations cooled the skin up to an hour of post-application, but the effect appeared to be independent of the concentration. Furthermore, the surrounding skin area did not cool significantly⁸.

Aim of the study

The aim of our study is to investigate local changes in skin characteristics during and after a topical application of a warming or cooling product without medicinal ingredients using non-invasive methods. Products with arnica or wallwort are excluded so as not to influence the subjective sensation of the subject. Products containing wintergreen oil, menthol or alcohol derivatives are included. The objective parameters are the perfusion of the microcirculation of the skin, the formation of erythema, the skin surface temperature, the oxygen saturation of the superficial muscles and the subjective perception of the subject. The parameters are collected as a baseline before the application of the product, then directly in the postal application at 0 min, then in 10-minute intervals up to one hour of postal application. Thus, 8 measurement moments take place. The aim is to record the local changes in skin characteristics during and after a topical application and to recognize the effects of the products. The current state of scientific knowledge requires further studies with topical products without medicinal ingredients in order to substantiate or refute the effects already established.

3.2 Medical product and indication

Topical ointments/creams/gels with a warming or cooling effect are used as over-the-counter products. The indication area of the warming ointments includes acute or chronic complaints of the musculoskeletal system in closed wound or skin conditions (including rheumatic pain, muscle bruises, muscle cramps). The indication for a cooling product is a reduction in swelling after acute injuries or pain (e.g. joint sprains).

3.3 Preclinical evidence

Xu et al. 2014 showed in their clinical study that laser speckle imaging can be used to visualize a change

SUPSI

in skin blood flow after the application of a warming ointment¹⁴. Lasanen et al. 2016 reported that the cooling effect of the skin is independent of the menthol concentration in the applied gel, and that the surrounding tissue does not experience significant cooling⁸.

3.4 Current clinical evidence

According to the authors' knowledge, there are currently hardly any clinical studies that investigate the effects of topical application of a warming or cooling product without an active pharmaceutical ingredient. The majority of existing studies are limited to topical products with the ingredient diclofenac.

3.5 Medical product: method of application in the study

The product to be applied is applied to the skin in an exactly measured amount (3g) on a given area (10cm x 10cm) on a lumbar paravertebral side of the skin. The procedure is carried out in a standardized way, by the same person.

3.6 Peers

Topical application versus no application

The test subject receives the product to be applied paravertebrally on one side, while the other side acts as a control. All test subjects are measured under the same environmental factors, the products to be applied are applied in the same way, quantity and technique.

Randomization

Randomization takes place with regard to the application side and the product to be applied. The application is paravertebral one-sided, the opposite side acts as a control. The allocation is made by drawing a lot.

The data obtained in this way is pooled accordingly after the application.

3.7 Risk / Benefits

Possible risks when using topical substances on the skin are spontaneously occurring skin redness with and without itching. If you are intolerant to an existing ingredient, an allergic reaction can occur. Furthermore, the participants can feel a feeling of warmth or cold in the application area. Subjects who may be at risk are recorded by the screening process and are not included in the study. Participants do not derive direct benefits from participating in the study. More information on securing the test subjects can be found in chap. 8.1.1. Justification

SUPSI

for the choice of population

This series of studies will be conducted with healthy adults, following on from previous studies^{8,9}. The physiological responses of the tissue to topical applications are assumed to be probable in this population of subjects.

Inclusion Criteria

- Adults aged 18 to 40 years
- No surgical interventions on the musculoskeletal apparatus in the area of the trunk
- Injuries to the trunk that occurred more than a year ago and do not cause any symptoms (pain at rest or during exertion, swelling, redness, restriction of movement of the adjacent joints)
- Closed skin and scar conditions

Exclusion criteria

- Age over 40 years
- Surgical interventions on the musculoskeletal apparatus in the area of the trunk
- Current injuries of any kind (skin abrasions, burns, sprains, muscle or tendon strains, bruises, fractures) in the area of the trunk that are still symptomatic
- Injuries to the trunk that were not more than a year ago and/or still cause symptoms
- Scars in the lumbar back area
- Fear of application
- Regular intake of medication (including self-purchased medication), with the exception of contraception drugs
- Metal implants in the area of the trunk (neck C7 to pelvis, sacrum and hip)
- Known allergies to the ingredients of the topical application (wintergreen oil, menthol, alcohol)
- Lack of skin ability to discriminate in the lumbar area epicritically and protopathically (pointed-blunt, warm-cold, sense of vibration)
- Renal failure
- Bronchial asthma
- Pregnancy / breastfeeding
- Diabetes mellitus type 1 or 2
- Polyneuropathies

The test subjects are comprehensively informed about the course of the study and possible risks before they are accepted to participate in the study. You will also receive the information in written form and have the opportunity to ask questions if anything is unclear. The declaration of consent explains to them what their rights and obligations are when participating. In addition, they are informed that they may withdraw from participation at any time without giving reasons, without incurring any disadvantages as a result. To clarify possible as yet unknown intolerances to an ingredient of the topical application, the product is tested on a small isolated skin area on the volar forearm, away from the actual application area to avoid interference. If there are positive signs of intolerance (including excessive redness, Local change in skin characteristics during and after a topical application of a warming or cooling product Version 04-24.06.2019

SUPSI

urticaria, itching, local swelling), the subject will be excluded from the study for safety reasons.

SUPSI

4 STUDY OBJECTIVES

4.1 General objectives

The general objectives of the study are to investigate the local changes in skin characteristics in the application area during and after a topical application of a warming and cooling product without a drug ingredient. In addition, the changes in the skin characteristics in the adjacent area of the application area are observed. The data provide information on the mode of action and the radius of action of the topical applications. All measurement methods are non-invasive, as is the application.

4.2 Primary objectives

To investigate the local changes in the skin characteristics in the application area during and after a topical application of a warming and cooling product without a medicinal ingredient.

Objective parameters:

- Perfusion of skin microcirculation (perfusion flow rates in arbitrary units)
- Erythema formation (a^* parameters in arbitrary units)
- Skin surface temperature ($^{\circ}\text{C}$)
- Oxygen saturation of the superficial muscles (%)

Subjective parameters:

- Information on local temperature perception and thermal comfort (9-point scale or 5-point scale)

4.3 Secondary Objectives

To investigate the local changes in skin characteristics in the surrounding tissue during and after a topical application of a warming and cooling product without a medicinal ingredient.

Objective parameters:

- Perfusion of skin microcirculation (perfusion flow rates in arbitrary units)
- Erythema formation (a^* parameters in arbitrary units)
- Skin surface temperature ($^{\circ}\text{C}$)
- Oxygen saturation of the superficial muscles (%)

Subjective parameters:

- Information on temperature perception and thermal comfort in the surrounding tissue

4.4 Other safety aspects (long-term)

Apart from the possible directly occurring skin intolerance reactions, which were not recognizable in the screening test, to an ingredient of the topical applications and the feeling of heat or cold, no long-term risks are to be expected.

SUPSI

5 STUDENT OUTCOMES

5.1 Primary outcomes

Perfusion of skin microcirculation

The perfusion of the skin microcirculation is visualized using the Laser Speckle Contrast Imager and the X-Flow ultrasound.

Laser Speckle Contrast Imager:

The "moorFLPI-2 Full-Field Laser Perfusion Imager" measures blood flow measured in flow rates (arbitrary units) of the skin's microcirculation. The laser is intended for clinical and physiological research. The fabric is illuminated with a divergent infrared laser beam. The laser measures down to a depth of 1mm, so it mainly detects the superficial blood flow, speed and concentration of red blood cells.

Ultrasound X-Flow:

The electronic MyLabClass C ultrasound device measures blood flow using the Doppler principle.

In the sub-analysis, the High Power Laser Doppler Monitor (moorVMS-LDF1-HP, moor instruments, www.moor.co.uk) is also used.

High Power Laser Doppler Monitor

The High Power Laser Doppler Monitor records the perfusion of the skin microcirculation up to the vascular capillary bed. The measurement method is non-invasive and is based on the laser Doppler principle. The sensors are placed on the skin area to be measured, which detect the perfusion of the skin microcirculation (blood flow, speed and concentration of red blood cells) within a few seconds.

Erythema formation

The erythema formation is visualized by means of the chromameter.

Chromameter:

The "Chromameter CR 300" from the manufacturer Konica Minolta performs tri-stimulus colorimetry. In this way, it measures the reflection and absorption of the fired light flashes in the tissue. By measuring the a* parameters, the extent of erythema can be quantitatively recorded.

Skin surface temperature

The surface temperature of the skin is measured by means of an infrared thermometer and the i-buttons. In addition, a thermal imaging camera records the skin surface temperature.

Infrared thermometer:

Local change in skin characteristics during and after a topical application of a warming or cooling product Version
04-24.06.2019 Side 29 from 53

SUPSI

The "Voltcraft Infrared Thermometer IR 800-20D" measures the infrared energy emitted by a body.

i-Buttons:

The sensors are glued to the skin, measure and store the skin temperature. The i-buttons are then read out with software developed for this purpose (www.ibuttonlink.com).

Thermal imaging camera:

The thermal imaging camera from Flir measures the surface temperature of the body using an infrared camera (www.flir.com).

Oxygen saturation of the superficial muscles

The oxygen saturation of the superficial muscles is determined in the sub-analysis using near-infrared spectroscopy.

Near-Infrared Spectroscopy moorVMS-NIRS:

Near-infrared spectroscopy makes it possible to record the absolute concentration of oxygenated and deoxygenated hemoglobin in human tissue down to a depth of 30 mm. Thus, the oxygenation of subcutaneous tissue structures (e.g. muscles) can be measured non-invasively. In contrast to the Moxy (Muscle Oxygen Monitor), the NIRS provides more stable readings in less time, which on the one hand guarantees more precise readings and on the other hand only touches (and disturbs) the skin area to be measured for a short time.

Subjective Perception Parameters

The test subjects indicate their subjective temperature perception on a 9-point scale from -4 (very cold) to +4 (very hot). They then rate the thermal comfort between 0 (pleasant) and 4 (extremely unpleasant) on a 5-point scale.

5.2 Secondary outcomes

As secondary results, the effects on the tissue area immediately adjacent to the area of application are examined analogous to point 5.1.

5.3 Security considerations

No further results are recorded that would serve safety.

Discontinuation of the experiment is the responsibility of the examiner with regard to the subject's subjective feelings and expressions.

If a test subject does not feel well during the application according to his or her subjective assessments, he or she can discontinue the experiment and withdraw participation in the study without any disadvantages. Distilled water and wipes are available within easy reach to wipe the product, as well as cold packs to alleviate possible skin irritation.

SUPSI

6 STUDIENDESIGN

Study design and justification

Randomized, controlled, clinical trial

This is a category A intervention study (ClinO, Art. 20), in which a tested and over-the-counter product is tested on healthy volunteers. The group size is $N = 90$.

For the planned continuation of the study within the framework of the sub-analysis described above, the recruitment of further $N = 15$ is planned. Thus, the total group size of the entire project increases to $N = 105$.

6.1 Method for minimizing influencing factors

6.1.1 Randomization

The area of application is randomized, right-sided or left-sided paravertebral lumbar. In addition, the assignment to the group "warming ointment" or group "cooling ointment" is hidden and randomized. The randomization procedure is carried out by lottery.

6.1.2 Blinding

Blinding of the subjects is possible with regard to the topical application of warming versus cooling, but not with regard to the control area, which remains blanco.

It is not possible to blind the applicator, but it is possible to blind the assessor of the primary and secondary results.

In addition, the blinding of the statistician can be guaranteed, who has no access to the personal data of the test persons and is not present during the data collection.

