
Measurements and procedures:
	
After the 20-minute acclimatization phase, the application area is drawn (skin-friendly pen), the template (recess 10cm x 10cm) is applied and the baseline measurements (a-e) are performed. After the baseline measurement, the product is applied (3g)⁸. The product is applied until it can no longer be distributed. The research employee wears a glove. This is followed by the measurements (a-d) at 0min, 10min, 20min, 30min, 40min, 50min, 60min post-application.
 
a) Perfusion of skin microcirculation
 
The perfusion of the skin microcirculation is performed using the Laser Speckle Contrast Imager (moorFLPI 2, moor instruments, www.moor.co.uk), the High Power Laser Doppler (moorVMS-LDF1-HP, moor instruments, www.moor.co.uk) and the ultrasound X-Flow (esaote MyLabClassicC, Maastricht, Netherlands, www.esaote.com). Since the contact gel, which is required for the ultrasound X-Flow measurement, could interfere with the product application, or could interfere with the subjective temperature perception of the subject, the ultrasound measurement is only measured at the time of baseline and 60min post-application. This was after questioning the subjective parameters.
 
b) Erythema formation
 
Erythema formation is visualized using the chromameter (www.konicaminolta.eu). The chromameter measures the light reflection and absorption of the skin.
 
c) Skin surface temperature
 
The surface temperature of the skin is measured using an infrared thermometer (Votcraft InfraRed Thermometer, IR 800-20D) and the i-buttons. The iButton system consists of self-adhesive sensors that wirelessly transmit skin temperature information to a computer (www.ibuttonlink.com). In addition, a thermal imaging camera (www.csem.ch) records the skin surface temperature.
 
d) Oxygen saturation of the superficial muscles
 
The oxygen saturation of the superficial muscles is determined using the near-infrared measurement method (moorVMS-NIRS, moor instruments, www.moor.co.uk) The measurement is non-invasive and painless. The sensors are placed on the corresponding muscles.
 
e) Subjective Perception Parameters
 
The test subjects indicate their subjective temperature perception on a scale of 9 points from -4 (very cold) to +4 (very hot). They then rate the thermal comfort on a 5-point scale between 0 (pleasant) and 4 (extremely unpleasant)¹¹.
 
Further processing of the data
 
Windows uses Excel for data pooling and the graphical representation of the end data®.

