6.1.3 Other Methods

No other methods are used.

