6.3 Procedure for unblinding (code break)

Blinding the investigators and/or study participants is only permitted if an unforeseen incident or medical problems occur during or after the completion of study participation in a subject, which may be attributable to participation in the study.

In the event of incidents (AEs) that occur during or shortly after thermal application (within the first 24 hours) and can potentially be attributed to the application of the topical product, the principal investigator may, at his or her discretion, immediately waive the blinding of the study participant and the investigators present in order to ensure adequate treatment of the study participant.

In the case of incidents (AE) that occur more than 24 hours after the application of the topical product, clarification with a physician is mandatory and a medical certificate is required for the removal of blindness. Data may then also be passed on to the attending physician with the consent of the study

SUPSI

participant concerned. This approach is justified because with the topical products used here, no life-threatening incidents are to be expected after the intervention due to these applications.

SUPSI

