7.3 Group assignment

The group allocation (warming product, cooling product) is concealed by means of a lot in a sealed envelope, which is drawn under the supervision of the study leader. The product to be applied and the side of the application area are noted on this lot. The examiner determines the examination condition and only passes on the subject number to the assessor. At the end of the entire data collection, the auditor pools the data sets according to the application.

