12.2 Data management

12.2.1 Data Management System

The raw data of the perfusion of the skin microcirculation (Laser Speckle Contrast Imager, Ultrasound X-Flow) are processed with the software "moorFLPI-2 full-field laser Perfusion Imager V1.1" and "esaote MyLab". The erythema formation is measured with the chromameter and read by the display device and transferred by hand to the raw data sheet. The skin surface temperature is also read from the digital display of the infrared thermometer and transferred by hand to the raw data sheet. The i-buttons are read out with the i-Button MMT software. The data from the thermal imaging camera is processed with the "Flir Research IR max" software. The oxygen saturation values of the muscles are stored on a PC by the software provided for this purpose by the company Swinco (PeriPedal v2.4.8). The subjective perceptual parameters with regard to temperature perception are asked orally and the answers are transferred by hand to the raw data sheet.

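### Assessor blinding can cover at most warming versus cooling; it cannot cover treated versus control side, which is the contrast in every hypothesis

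*Combined protocol and SAP*

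**What the plan says.** Section 6.1.2 treats three roles differently. Subjects can be blinded to warming versus cooling, "but not with regard to the control area, which remains blanco". The person applying the product cannot be blinded. For the assessor, the text says "it is possible to blind the assessor of the primary and secondary results", with no restriction on the contrast.

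Section 7.3 supplies the mechanism. The lot carries both the product and the side; the examiner knows the condition and "only passes on the subject number to the assessor". Section 6.1.3 adds "No other methods are used". Section 6.3 treats the blind as operating during the session, since the principal investigator may "immediately waive the blinding of the study participant and the investigators present".

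In the synopsis (Measurements and procedures), "the application area is drawn (skin-friendly pen), the template (recess 10cm x 10cm) is applied" before the baseline readings. Section 9.2.2 (items 2.1 to 2.3) says that the area drawn is the randomized one, that 3 g is spread over it, and that the first follow-up reading comes directly afterwards. Under 8.2.2 the opposite side receives nothing.

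Section 12.2.1 says chromameter values are "read by the display device and transferred by hand to the raw data sheet" and describes the infrared thermometer in the same way. The perception answers "are asked orally and the answers are transferred by hand to the raw data sheet".

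**The concern.** A blind is useful only for the comparison that it hides. Here that comparison lies within the subject, between the treated and the untreated side. Withholding the lot keeps written information from the assessor, but the side can be seen on the back. If the person taking the readings knows the side, expectation can enter through where the instrument is placed, which reading is accepted, how a value is copied, or how a question is put. At stake is whether these primary outcomes can be described as blind-assessed for the contrast that is tested.

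**Working it through.** No stated figure bears on this point: section 11.2 gives no effect size, standard deviation or power. The check sets the sections side by side.

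1. **Contrast tested.** Section 11.1 has five outcomes for each of two product classes, so 5 × 2 = 10 pairs of hypotheses. All ten refer to the opposite side, and Factor 1 in 11.4.2 is product versus control. None compares warming with cooling.

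2. **What the mechanism hides.** The lot names product and side (7.3). Withholding it can hide the product class. It hides the side only if nothing at the bench reveals it.

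3. **What is visible at the bench.**
   - Outline: the randomized area is drawn before baseline (synopsis; 9.2.2, item 2.1). A matching outline on the control side is not described.
   - Product: 3 g on 10 cm × 10 cm is 3,000 mg / 100 cm² = 30 mg/cm². The first reading follows directly, and no wiping-off beforehand is described.
   - Control side: bare, with no vehicle or sham (8.2.2).
   - Response: erythema is itself an outcome (5.1), so redness may show the side at later readings.

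4. **Masking of the person at the skin.** None is described, and 6.1.3 excludes further methods.

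5. **Which measures are exposed.** Section 12.2.1 describes data handling for seven instruments: laser speckle, ultrasound, chromameter, infrared thermometer, i-buttons, thermal camera and muscle oxygen. Two of the seven (chromameter and infrared thermometer) are read off a display and copied by hand; so are the oral answers. The other 7 − 2 = 5 go through software, which removes copying as a route for bias but not sensor placement or region choice.

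6. **Does the baseline reading remove the problem?** A constant bias tied only to the outline would be present at baseline as well and would cancel in the side-by-time interaction. The product and redness appear only after application, so a bias tied to them would not cancel.

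The stated blind therefore does not extend to the contrast in step 1.

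**The case against.** The best defence is that 6.1.2 says only that assessor blinding is possible, in a paragraph that has just referred to warming versus cooling, while 7.3 speaks of concealing the group allocation. On that reading the intended blind was to product class, and the fault is one of wording. This is plausible, but the limit is never written for the assessor, although it is written for subjects. The withheld lot also carries the side, and 6.3 treats the blind as real. The wording needs correcting on either reading.

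Several stronger readings are tempting and are not supported:

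- **That the assessor is shown to copy the values.** Section 12.2.1 names nobody. An assessor working only from coded data is not excluded, though none is described, and someone must still take the readings at the skin.
- **That only the treated side is outlined.** Section 8.1.2 has the control area measured under the same protocol, so a matching outline is not ruled out. It would remove one cue, not the product or redness.
- **That scent, or gel lasting the full hour, reveals the side.** The documents mention no scent and do not describe residue at 10 to 60 minutes.
- **That image regions are drawn after the response is visible.** The documents do not say when they are drawn.
- **That the false-positive rate rises by a stated amount.** Any such rate needs an assumed observer shift and a single paired test. The documents give no shift, and 11.4.2 plans a repeated-measures analysis.

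Two further points stand. Both hand-copied devices show a digital number, so the routes for bias are placement and transcription rather than judgement. And 6.1.2 already discloses that subjects cannot be blinded to the control area, so for the scales only the part played by the person asking is new.

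**Conclusion.** The concern holds in a limited form. Assessor blinding can apply at most to warming versus cooling, and none of the ten hypothesis pairs tests that. Even this is an upper limit, since Table 1 schedules warming products in 2017 and cooling products in 2019. For treated versus control side, nothing described keeps the person at the skin unaware.

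The conclusion rests on two inferences: that someone takes the skin readings in view of the back, and that product is visible at least at the reading directly after application. Exposure is greatest for a*, the infrared thermometer and the oral scales, and smaller for software-logged measures. The size of any bias cannot be derived from the documents, and they do not show that any result is in fact biased. The trial can run as designed; the blinding statement should be corrected and the avoidable exposure reduced.

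**What to change.** 1. In 6.1.2 and 7.3, limit assessor blinding to product class and state that assessment is not blind to side.
2. For laser speckle and thermal images, draw mirror-image regions on each subject's pre-application baseline image, covering the application area and the 5 cm surrounding zone. Apply them unchanged to all seven later images, with a check for subject movement. Region choice then cannot depend on the response. Apply the same rule to stored images of subjects already measured.
3. Report a*, infrared thermometer and subjective-scale results as not blind to side.
4. For subjects still to be measured, outline both squares identically before the lot is opened. This removes one cue only and cannot be applied to the warming-product subjects whose data collection Table 1 places in 2017.

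The cost is protocol wording, one extra outline per remaining subject and slightly more image processing; no new device is needed. The downside is that the trial can no longer claim blinded assessment of the treated-versus-control contrast.
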